Also see Risk Assessment in Appendix. In addition, the lead researcher will remain as contactable throughout the project and will provide advice, risk assessment and signposting throughout the project. At the outset of each group and as part of group agreement and rules, all participants will be made aware of the need to speak to the facilitators should they experience any significant adverse physical or emotional difficulties requiring further medical or psychological attention.

i. Are there any potential risks or adverse effects to participants?

As well as any physical risks or adverse effects, you should consider the potential for discomfort, distress, inconvenience or change in lifestyle for the participants, and explain how these will be managed.

See Risk Assessment

ii. Are there any particular requirements or abstentions that will be imposed on participants? (Eg. multiple attendance sessions; abstention from alcohol, tobacco, etc.).

Participants will be required to attend all 8 sessions of the mindfulness course and will be classed as completers with a minimum of 6 sessions.

Participants will be required to abstain from alcohol, illegal or otherwise mentally impairing substances.

Participants will be required to keep a log of their personal-time practice, read the appropriate course manual/book and complete their home mindfulness practice.

iii. Are there any potential benefits to participants, or to the wider society?

Given the evidence presented earlier and the broader evidence of mindfulness, the current costs of attending mindfulness courses, participants will be able to complete a full and Breathworks accredited Stress or Pain Course, which also provides the basis for future mindfulness teacher training in line with current UK standards. These courses would usually retail in the region of £190-£350 per head.

As the courses will be offered to a community sample, this will not prevent patients with chronic pain from accessing the current provision at the local pain management centre. In actual fact, it will give opportunity to more people to access both stress and pain courses.

Above and beyond the benefits to understanding research, they will contribute to furthering understanding, improving provision of pain specialist services and to pain professionals competency standards.

The benefits of mindfulness go beyond pain and include those to the workplace, team working, productivity, stress and performance and general wellbeing.

iv. Are there any potential risks or adverse effects to *researchers themselves*?

Given the open recruitment via social media, there is the potential risk of unknown participants' forensic or problematic history. However, this will be mitigated by requesting all participants seek to access the research project via initial contact with their GP surgeries.

v. Where samples will be taken from the participant, please state which samples, the amount and frequency of them and whether the sample would be taken as part of the normal patient care or specifically for the purposes of the research? If a sample would normally be taken as part of usual patient care - will the amount taken be any greater due to the participation of the participant in the research?

Not applicable

vi. Where the research involves the use of radioactive isotopes, please confirm that the dosage proposed to be used in the research has been approved by a Radiological Safety Committee or Administration of Radioactive Substances

Advisory Committee (ARSAC), and that the person(s) who will administer the dose is/are properly qualified and hold(s) the necessary certificate(s)?

Not applicable.

- vii. Where the research involves the testing of a medicinal product (or medical device), please state the regulatory status of the drug/device in question. Is the research being conducted under the terms of a product licence, Clinical Trials Certificate (CTC), Clinical Trials Exemption (CTX) or Doctor's and Dentist's Exemption (DDX)?**

Not applicable.

- viii. Please indicate whether participants will receive payment or reimbursement for taking part in the research study (including reimbursement of expenses). If so, what amount?**

Not applicable.

- ix. Please state the relationship, if any, which may/will exist between the researcher(s) and potential participants. (Eg. will any of the participants be students, subordinates or colleagues of the investigator, or staff members of the University?)**

Not applicable. However, given the nature of Jersey, participants may be known to the research team, may be acquaintances or fellow colleagues. This is unavoidable.

4. Informed consent:

Will informed consent be obtained from the research participants?

Yes No

If 'YES', please give details of who will obtain consent and how this will be done, including how long participants will have to decide whether or not to take part. If 'NO', please explain why not.

Participants will be initially approached with support of GP practices and local social media pages for working age adults (18 yrs and above), given that chronic pain speciality in children and young adults is a speciality within itself.

Potential participants will have two weeks to contact the researchers for questions and to consider opting-in.

Children

Can you confirm that, where the participant is 16 years old or over, consent to participate in the research will be obtained from the young person themselves.

Yes (but not applicable in this project) No

Can you confirm that, where the participant is under 16 years of age but is judged to have the maturity and capacity to understand the nature of the research, consent to participate in the research will be obtained from the young person themselves.

Not applicable.

Please state the manner in which any apparent objection to participation by a minor will be handled.

Not applicable.

Please state whether and how parental consent, or consent of the legal guardian or order/declaration of the court, will be sought in relation to the participation of minors.

Not applicable.

*NB. Copies of the consent form(s) and Participant Information Sheet(s) to be used in the research **must** accompany this application.*

5. How will participants who may not adequately understand verbal explanations or written information given in English be enabled to consent?

Not applicable. Given the resource for this project, the potential confounding effects to the wider group and the manner in which groups are delivered, it will be a requirement for potential participants to be able to understand verbal, written explanations and in English.

6. Please state what measures will be taken to ensure that participants are able to withdraw from the research at any time without explanation and without fear of reprisal should they so wish

This will be included in the consent form.

7. Confidentiality of data:

What measures will be taken to protect the confidentiality of participants' data?

You should consider data in hard copy, electronic and audio/audio-visual form. You should explain how the anonymity of participants is protected during the data collection process, during data analysis and at the end of the research project.

All participants will be allocated a participants number/code to protect their identity and databases will be anonymised, once paper/online survey data is submitted by the participant. The data will be anonymised before being shared with the university statistician.

All data will be stored/shared within SOJ or appropriately encrypted USB storage devices and University

Who will have control and act as custodian of the data used in / generated by the research?

The lead researcher.

Can you confirm that the data will be retained in accordance with the Data Protection (Jersey) Law 2005 which states that "data shall not be kept for longer than is necessary"?

- Yes, I confirm that data, with regard to computer storage and processing of participants' personal information, will be stored securely and confidentially for no longer than is necessary and comply with the Data Protections (Jersey) Law 2005. As far as possible, the data supplied and generated during the course of the study will remain confidential.*

8. Vulnerable groups:

Are you *specifically recruiting* participants from any of the following groups?

- | | |
|--|--------------------------|
| Children under 16 |  |
| Pregnant women |  |
| The elderly |  |
| Persons suffering from mental disorder |  |
| Adults with learning disabilities |  |
| Prisoners |  |
| Young offenders |  |
| Other vulnerable groups |  |

Please explain why it is necessary to conduct research involving such participants, and whether the required data could be obtained by any other means.

Not applicable

Please state what special or additional arrangements, if any, will be applied, particularly in relation to Participant Information Sheets and gaining informed consent, to safeguard the interests of such participants.

Not applicable

Please state whether, and if so, how participation in the proposed research may/will be of personal benefit to individual participants.

As above

9. Disclosure statement:

If you are working with vulnerable adults or minors (under the age of 18 years old), please state whether or not you have applied for and/or received a disclosure statement from the Criminal Records Bureau (CRB).

Yes No

If 'YES', please give the disclosure number and date this was made.

Disclosure (certificate)
number:

00158412746E

Date of disclosure:

14/08/2017

Part 4: Financial and other arrangements

- 1. Please state any financial or other interests (including any conflicts of interest) that the applicant, supervisor(s) or employer has in relation to the conduct of this research.**

The Lead Researcher is a Breathworks Accredited Mindfulness Teacher since 2013 and trainer since 2018. He is also an ACT practitioner and part of the Brewathworks Work Advisory Group (2018). However, given the project will evaluate the data utilising both Breathworks packages as active interventions, and with equal provision of both packages, there is not a direct preference for a given therapeutic approach. Breathworks have agreed to support financially the project and contribute to assessing the fidelity of the interventions provided. However, the analysis of data will be performed blind by [name] at LJMU, in order to manage any potential conflict. There is no financial incentive or reward for the applicant, supervisor or employer in conducting this research.

- 2. Please state the amount of payment, if any, that will be paid to the researcher(s) [over and above their normal salary].**

None

- 3. What additional costs will be incurred by HSSD through the conduct of the research, and how are these to be met? Please state the details of any funding which has been secured for the research.**

Currently Breathworks are considering the funding of two teachers to deliver the mindfulness interventions (flights, accommodation and subsistence), estimated to be in the region of £8000 plus £8160 in travel, accommodation and subsistence costs.

We have also applied for in the region of £13000 to cover the qualitative analysis of the

data. Failing that, we will utilise trained volunteers and support from University (See *Clulow application form*).

The pain clinic lead and project sponsor, [name], has agreed for the project to be part of the Pain Clinic research work that forms part of the lead researcher and assistant psychologist / research assistant remit, and therefore, as part of the job plan of both members of staff. It is also in line with the pain clinic strategy around contribution to teaching and training on self-managing pain in Jersey. We have however showed the monetary value of this contribution as part of any requests for support and grant requests.

[name] has agreed to fund materials (books that are used as course manuals, stationery for psychometric and interview material, floor mats, refreshments and utilisation of group room within the premises outside of the times used by the clinics regular courses). The anticipated cost of books is in the region of £1000, mats & stationery £200 & refreshments £40 Total: £1240

Stationary costs will be will be mitigated with the use of online survey tools where possible (surveymonkey).

4. What arrangements are in place for monitoring the conduct of the research, and dealing with any issues, complaints or adverse effects which may arise from the research?

[Note that, in the first instance, complaints should be addressed to the Academic Research Supervisor or the sponsoring Head of Department]

The lead researcher will be the point of contact for any adverse effects (distressing thoughts or emotions) arising from the intervention. However, to mitigate this, no participant with current diagnosis of PTSD or active psychiatric condition requiring treatment, or drugs and alcohol dependence will be accepted on the trial (part of the exclusion criteria) as part of the recruitment process.

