However, numerous methodological and contextual limitations exist within the context of pain management centres that are increasingly providing mindfulness based interventions to pain sufferers. This has potential implications for whether implementing mindfulness skills is done with clarity, good governance about whether, where and how it is helpful, or whether it even can be harmful, duplicate other treatments or unnecessarily burden pain sufferers with something that is not needed. In this context, it also has significant implications on any required development of teachers' competencies.

No current research has attempted to unify ACT and other mindfulness process measurement (how people get to change – as opposed to what change they achieve) or to establish the potential contribution and relevance of different specific mindfulness courses in chronic pain patients' treatment pathways and outcomes.

A community-based multidisciplinary-pain-management naïve sample (N=100) of chronic pain patients will be recruited in primary care and placed on a time-set waiting list and then randomly allocated to **one** of two standardised active online mindfulness treatments - stress **or** pain group

conditions. Measurement will include theoretically validated process and outcome measurement. Treatment adherence and fidelity will be independently evaluated from recorded sessions and inter-rater agreement checks performed.

Quantitative analysis will be performed to include descriptive statistics, analysis of variance, session-by-session process change trends, and post-hoc analysis on GP and A&E visits.

Qualitative thematic analysis will complement and bolster the findings of the quantitative phase to include additional process variables unaccounted for by the ACT model, patient experience and descriptive comparison of the two active conditions, including descriptive statistics comparing frequency of reported themes between the two treatments.

i. Aims and objectives:

This study aims to explore and better understand the contribution of standardised group-based mindfulness courses to theoretically valid and coherent mindful-change processes.

OBJECTIVES

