- Utilising the same 'dosage' and type of interventions (groups with similar structure, delivery times and requirements for practice) utilising MfH-MBPM and MfS (Burch and Penman 2013, Hennessy 2017)
- Using appropriate psychometric and qualitative analysis and targetting of explicit process-change.
- Reporting adverse side effects
- Measures in line with IMMPACT recommendations for research on chronic pain (Dworking *et al.*, 2005).

iii. **Study design, to include recruitment and sampling strategy, inclusion/exclusion criteria, sample size and justification:**

In order to address the research questions, the current study will be divided in and presented as separate quantitative and qualitative components:

Quantitative study:

Design and Method

DESIGN

A waiting-list controlled, randomised, pilot trial of mindfulness based group treatment comparing two active standardised interventions (mindfulness for stress vs. mindfulness for pain/health)

SETTING AND STUDY POPULATION

An opportunity sample via general practice, waiting-room advert and GP supported recruitment in Jersey, serving a population of 106,000, will be invited to take part in the study.

RECRUITMENT

All general practices in Jersey will be invited to take part in this study. They will be recruited through the Jersey Primary Care Body and Social Media Advertising.

CASE IDENTIFICATION

Over a six months period.

Once potential participants have consented, searches will be run on GP electronic health records to identify suitability. Demographic data including gender, age, ethnicity and employment status, pain diagnoses, current medication and dosage, co-morbidities and mental health diagnoses will be extracted via GP referral to the study, including that the patients meet inclusion criteria and do not meet any of the exclusions.

INCLUSION AND EXCLUSION CRITERIA (PATIENTS)

Inclusion criteria:

1. Pain > 3 months
2. Ability to communicate and literacy in English
3. Age 18 years or older
4. No current outstanding medical tests or procedures for conditions expected by the GP to interfere with participation in treatment.
5. Has not previously received non-medical treatment at a specialist pain centre, or

attended a multidisciplinary pain management programme.

6. Ability to utilise online video conferencing technology (i.e. ownership of a compatible device & necessary technical competence)

Exclusion criteria:

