7. Patients who are actively suicidal, terminally ill or have dementia, cognitive impairment, learning difficulties, or the GP knows of another reason to exclude.

ETHICAL ISSUES

Informed consent

We will obtain approval to contact practices regarding the study with participant's information leaflet and GP information leaflet. We will also obtain informed consent from the treatment providers, including in relation to video/audio feed being recorded. Participants will be offered opportunity to switch off their cameras.

Confidentiality

Data will not be accessed outside the research team. Once collected, checked for inclusion criteria and allocated to a randomly generated participant number, data will be anonymised and prior to the off-site transfer for blind analysis (the statistician will not be aware of which condition stress/pain the participants have been allocated to). Data Transfer Protocols will be utilised in line with the Government of Jersey Governance and Data Protection system, to transfer the data ahead of analysis.

A participant waiting-list randomised, pilot trial of mindfulness based group treatment comparing two active interventions (stress vs pain mindfulness courses) and the waiting-list at recruitment time and 8-weeks post recruitment, coinciding with the start of treatment.

Randomisation will be based on computer-generated random numbers and the sample randomised, will act as a pseudo-waiting-list control for the eight-week waiting period ahead of the intervention.

Recruitment details and Participants

PARTICIPANTS AND DATA COLLECTION

100 people with chronic pain (defined as > three months duration) will be recruited from primary care and social media adverts in Jersey (the social media participants will be

required to register their interest via their GP who will then refer to the lead researcher). Once recruited, participants will be required to complete baseline outcome and process measures, 8-weeks ahead of beginning their 8-week course. Randomisation will take place at this point to either the stress or the pain course. They will repeat this assessment on week 1 of the course and then again at week 4. They will also complete only process measures weekly during the course, in order to explore for links between weekly course content and specific process change.

Posttreatment assessment will be completed within four weeks of treatment completion and at 3-month follow up.

How this study will improve on previous research

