4) *Cognitive fusion:* the Cognitive Fusion Questionnaire (Gillander *et. al*, 2014)

5) *Values:* The Chronic Pain Values Inventory (McCracken and Yang 2006)

6) *Committed Action:* The 8-item Committed Action Questionnaire (McCracken, Chilcot et al. 2015)

Outcome measures:

Pain Intensity and interference on quality of life : the Brief Pain Inventory – Short Form (Tan, Jensen et al. 2004), numeric rating scale (NRS) on intensity (scale 0-10) including, worst, least

average (in the past week) and right now. BPI interference scale for impact on quality of life.

Emotional Functioning

a. *Pain related distress:* The Pain Catastrophizing Scale (Sullivan, Bishop et al. 1995)

b. *Depression:* The Beck Depression Inventory – Fast Screen (Poole, Bramwell et al. 2009)

Global Impression of Functioning: the Patient's Global Impression of Change (Guy 1976) will allow to consider perceived improvement and deterioration.

Qualitative:

DATA ANALYSIS

Transcribed data will be managed with NVivo software. All transcripts will be read and reread to ensure familiarity with the data. We will use thematic analysis (Braun and Clarke 2006) to identify recurring themes across the data and examine relationships between themes. The thematic analysis will be undertaken by two researchers independently coding for emerging themes and then comparing codes and themes.

TOPIC GUIDE

Do you have any previous experience in taking part in clinical trials or medical research?

I'm really interested in finding out what were your initial expectations and feelings about the mindfulness course?

What do you feel you have gained from attending the course?

What (if any) changes have you noticed in your health/quality of life? [probe for anything getting better or worse: health, emotional, physical, practical]

How do you feel the course has contributed to how you manage chronic pain?

This study has involved you doing some reading, meditation and practices in everyday life ('habit releasers'). Would you give me a sense as to whether you have managed to engage in these practices? [Ask about how long typically they have practiced daily formal meditation; are they still practising?; What has stuck and what hasn't?]

Is there anything else you would like to say about your experience of the course?

How do you feel the teacher contributed to your experience of the course?

What contribution do you feel the group has made to what you have learnt?

Since attending the course:

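### Adverse-effect reporting is promised, but no adverse-effect question is put to participants, so harms are likely to be under-counted

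*Combined protocol and SAP*

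**What the plan says.** All references are to the combined protocol and SAP.

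- **Promise.** Part 3, section 2(ii), in the list of improvements on current research, includes "Reporting adverse side effects". The scientific abstract gives as part of the motivation that it is unclear how mindfulness helps "or whether it even can be harmful".
- **Facilitator route.** Part 3, section 3 (Potential to cause distress): participants are "made aware of the need to speak to the facilitators should they experience any significant adverse physical or emotional difficulties", and the sentence goes on to limit these to difficulties "requiring further medical or psychological attention".
- **Lead-researcher route.** Part 4, item 4: "The lead researcher will be the point of contact for any adverse effects (distressing thoughts or emotions) arising from the intervention". Part 3, section 3 also keeps this person contactable throughout the project.
- **Routine forms.** Part 3, section 2(iii) (Participants and data collection) places outcome and process measures at baseline, week 1, week 4, post-treatment and 3 months. For the other course weeks: "They will also complete only process measures weekly during the course".
- **Indirect signals.** Part 3, section 2(iv) includes the global impression of change, which "will allow to consider perceived improvement and deterioration", together with pain, catastrophizing and depression scales. The interview topic guide has a prompt about things getting worse.
- **Interview sample.** At most 30 people with a target of 10 per course, excluding those who attended fewer than 6 of 8 sessions.

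Neither the measures nor the analysis section contains an adverse-effect item, definition, severity grade or by-arm count.

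**The concern.** Harms are a stated deliverable, but what would be counted is left to spontaneous report. Both direct routes need the participant to decide that a problem is worth raising. The facilitator route sets a high threshold, and the lead-researcher route describes adverse effects in emotional terms only. Someone who feels worse and stops attending has little occasion to tell anyone, and that person is also outside the interviews.

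Two things are at stake. First, a low or zero count could be read as evidence of safety when it partly reflects not asking. Second, a participant who is worsening may be noticed late, or only after leaving.

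**Working it through.** **Step 1. Every described route by which an adverse effect could reach the data**

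| Route | Asked of participants? | Limit |
|---|---|---|
| Facilitators (Part 3, section 3) | No, participant must raise it | Significant difficulties needing further attention |
| Lead researcher (Part 4, item 4) | No, participant must raise it | Adverse effects glossed as thoughts or emotions |
| Global impression of change | Yes | No event, cause or severity recorded |
| Pain, catastrophizing and depression scales | Yes | Score changes, not events; during the course at weeks 1 and 4 only |
| Weekly forms | Yes | Process measures only |
| Interviews | Yes, probe for worsening | At most 30 people; under 6 of 8 sessions excluded |
| GP and A&E visits (post-hoc) | Counted | Compares the wait with end of treatment to follow-up; course weeks not included as written |

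The rows that solicit information do not record adverse events. The two rows that concern adverse effects directly do not solicit.

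**Step 2. Reach of the interviews**

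- Target 20, maximum 30 in total. Of 100 recruited: 20/100 = 20% to 30/100 = 30%.
- At the minimum target of 30 per arm (60 in total): 20/60 = 33% to 30/60 = 50%.
- Of those who attended fewer than 6 sessions: none.

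**Step 3. Illustration of size**

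The plan has no figure to reproduce: it gives no event rate and no power calculation. Let *p* be the true proportion of participants with an event, *c* the share captured, and *n* the arm size (50 planned, 30 minimum, from the Procedure paragraph). Both *p* and *c* are assumptions.

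Chance of recording no event in an arm = (1 − p·c)^n. For example, with p = 5%, c = 25%, n = 50: (1 − 0.0125)^50 = 0.53. With p = 10%, c = 75%, n = 50: (1 − 0.075)^50 = 0.02.

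| n | p | c = 25% | c = 50% | c = 75% | c = 100% |
|---|---|---|---|---|---|
| 50 | 5% | 53% | 28% | 15% | 8% |
| 50 | 10% | 28% | 8% | 2% | 0.5% |
| 30 | 5% | 69% | 47% | 32% | 21% |
| 30 | 10% | 47% | 21% | 10% | 4% |

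**Step 4. What a zero count could show even with full capture**

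One-sided 95% upper bound = 1 − 0.05^(1/n), which is 5.8% for n = 50 and 9.5% for n = 30. Better collection removes the under-count; it does not make the trial large enough to exclude uncommon harms.

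**The case against.** The strongest reply is that the sentence about speaking to facilitators is a safety instruction under ethical issues, not a data-collection method. Nothing there says these contacts are the source for the promised reporting. That stands: the plan states no collection method for adverse effects, and a reader should not infer that it deliberately chose a passive one. The gap remains, because nothing else described would produce the report.

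A reader might also infer that harms reach the team only through the facilitators. The documents do not support this: the lead researcher is a named contact, and the global rating, symptom scales and interview probe can all show worsening. They are indirect signals, however.

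Nor do the documents show that reporting would differ between arms. The instruction goes to all groups and teacher competence is to be matched. The option to switch cameras off does not stop anyone from making contact.

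Two practical objections also stand. Questionnaire burden is a stated concern in the research questions and the measures section. In chronic pain, a question about worsening will also pick up ordinary fluctuation. Finally, the participant information and consent pages were not available for this review, so any instruction there about reporting problems could not be checked.

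**Conclusion.** The point holds as an improvement worth making before recruitment. Adverse-effect reporting is promised, the text describes no solicited collection, and the direct routes rely on participants coming forward, so harms are likely to be under-counted, particularly among people who stop attending.

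The size cannot be derived from the documents. Under the assumed 5–10% true rate and 25–75% capture, the chance of an empty record in an arm of 50 is about 53% to 2%, against 8% to 0.5% with full capture. The width of that range shows how far the answer depends on the assumptions. It would be tempting to say that events will certainly be missed; without an event or capture rate, the documents support only a likely under-count.

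**What to change.** 1. **Item.** Ask whether anything has become worse or distressing, physically or emotionally, since the last form, with severity, free text and whether the participant thinks it relates to the course. Add a box to request contact. Use identical wording in both arms.
2. **Timing.** Put it on the existing week-1 form (covering the 8-week wait as a background rate), each weekly form, and the post-treatment and 3-month forms. A weekly item alone would miss the wait and the follow-up. The background rate is approximate, since one form recalling eight weeks is not the same as weekly asking.
3. **Coverage.** Send it to everyone randomised, including those who stop attending.
4. **Review.** Have the lead researcher read answers before the data are anonymised. This must be reconciled with Part 3, section 7, which anonymises databases once survey data are submitted; otherwise a contact request could not be acted on.
5. **Reporting.** Give the number and percentage of participants with at least one event, by arm, with 95% confidence intervals, beside the waiting-period figure. Add reasons for withdrawal where given.

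The cost is a slight addition to forms that already exist and are online where possible, staff time to read answers, and one table. Reported counts will be higher than under spontaneous report and will include ordinary pain fluctuation; the severity, attribution and waiting-period data help in reading them.
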